10.0 Statistical Considerations

10.1 Data Analysis

The patient population demographics will be descriptively summarized both combined and by treatment randomization. All analyses will be conducted under the intention-to-treat principle and all deviations and adverse events will be reported.

Our primary aim is to compare rate of wound complications (wound dehiscence or infection) identified within first month after surgery by treatment group (standard of care or NPWT). As this is a large randomized trial, the comparison will first be made using a Chi-squared test as we anticipate approximate balance in all measured and unmeasured confounders. These results will be supplemented using logistic regression, including demographics and clinical variables (including surgeon) as appropriate.

Our secondary aim is compare the time from surgery to starting adjuvant therapy among those with confirmed malignancies. This will be measured in days and will be available regardless if patients undergo treatment at our study facilities as their surgeon will manage their care and maintain contact up to 6 months regardless of follow-up location. The effect of NPWT on the length of the number of days until treatment will be assessed using Poisson regression, adjusting for over-dispersion if necessary. As stated above, we will supplement these results adjusting for demographic and clinical variables as appropriate.

For all analyses, p-values of less than 0.05 will be considered statistically significant and will be performed using SAS software version 9.3 (Cary, NC).

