10.2 Sample Size Calculations

As stated in the Section 4, we retrospective chart review of this patient population found 25% rate of wound complications. Group sizes of 97 each (194 total) achieves 80% power to detect a difference between the group proportions of -0.15; in other words, assuming the standard of care group has a complication rate of 25%, we could detect a complication rate in the NPWT group of 10% as being statistically significantly lower using a two-sized Z-test with a significance level of 0.05. This represents a clinically significant change in complication rates while remaining a feasible number to recruit within the study sites. Our proposed sample size is therefore 200 (100 in each group).

The secondary aim is not to formally test hypotheses but rather to describe this outcome and calculate preliminary estimates of differences. Among women undergoing this procedure at our study sites, approximately 70% will be

diagnosed with a malignancy, resulting in a sample size of 140 for this analysis. Among women in the standard of care group, we anticipate they will begin adjuvant therapy within 4-6 weeks after surgery. This sample size is more than sufficient (>90% power) to detect a difference of 1 day in time between surgery and beginning adjuvant therapy.

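### The Poisson analysis of days to adjuvant therapy corrects its variance for over-dispersion only, so intervals would be too wide if starts cluster within 4-6 weeks

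*Combined protocol and SAP*

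**What the plan says.** Section 10.1 defines the secondary outcome as time from surgery to the start of adjuvant therapy among patients with a confirmed malignancy. On the unit it says: "This will be measured in days and will be available regardless if patients undergo treatment at our study facilities". The effect of NPWT on that number of days "will be assessed using Poisson regression, adjusting for over-dispersion if necessary". It names no link function, no robust variance and no rule for when the adjustment is needed. It sets a 0.05 significance threshold for all analyses.

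Section 10.2 gives the only information on the distribution: "Among women in the standard of care group, we anticipate they will begin adjuvant therapy within 4-6 weeks after surgery". It states neither a mean nor an SD. The analysis set is the patients "diagnosed with a malignancy, resulting in a sample size of 140 for this analysis". The purpose is set out as follows: "The secondary aim is not to formally test hypotheses but rather to describe this outcome and calculate preliminary estimates of differences". The section then adds a power statement: "This sample size is more than sufficient (>90% power) to detect a difference of 1 day in time between surgery and beginning adjuvant therapy".

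**The concern.** Poisson regression takes the variance of each observation to equal its mean unless a scale is estimated or a robust variance is used. That can be reasonable for counts of events. For a duration, the spread depends on how patients are scheduled and delayed, and may fall on either side of the mean.

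The plan deals with one side. If the variance exceeds the mean, it allows an adjustment. If the variance is below the mean, nothing in Section 10.1 reduces the standard error, and the interval comes out wider than the data warrant. Since Section 10.2 says the aim is to "calculate preliminary estimates of differences", the interval around that difference is the main product of this analysis.

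**Working it through.** **Inputs.** From Section 10.2: a window of 4-6 weeks = 28-42 days, and 140 patients. Assumed: mean 35 days (the midpoint), 70 per arm (from 1:1 allocation), and the same distribution in both arms.

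**The plan's own figure.** Section 10.2 gives no standard error for this outcome, only power above 90% for 1 day. Under the named model:
- SE of the difference = sqrt(35) × sqrt(2/70) = 5.92 × 0.169 = 1.00 day.
- Power for 1 day = Φ(1/1.00 − 1.96) = Φ(−0.96), about 17%.
- Power of 90% would need an SD of at most 1/[(1.96 + 1.28) × 0.169] = 1.83 days. The variance is then 3.33, and 3.33/35 is a dispersion of about 0.10.

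The stated power therefore does not reproduce under the stated model. That is a separate matter. It is relevant here only because that claim would itself require strong under-dispersion.

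**Case A: the window describes individual patients.** Dispersion is variance/mean, and the width ratio is sqrt(35)/SD. Coverage is 2Φ(1.96 × ratio) − 1.

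| Reading of 28-42 days | SD | Variance | Dispersion | True SE | Width ratio | Coverage |
|---|---|---|---|---|---|---|
| Uniform | 14/sqrt(12) = 4.04 | 16.3 | 0.47 | 0.68 | 1.46 | 99.6% |
| 95% range | 14/3.92 = 3.57 | 12.8 | 0.36 | 0.60 | 1.66 | 99.9% |

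The 95% half-width is 1.96 × 1.00 = 1.96 days under Poisson, where 1.96 × 0.68 = 1.3 or 1.96 × 0.60 = 1.2 days would be right. The width ratio and coverage do not depend on the number per arm; the SEs do.

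The direction does not hinge on these two shapes. Any single-peaked distribution confined to 28-42 days has variance at most 14²/9 = 21.8, below even the smallest possible mean of 28. Only an extreme split between the two ends (variance 7² = 49) would exceed the mean.

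**Case B: a delayed tail.** Sections 1.0 and 3.0 say wound complications can delay adjuvant therapy, without giving the size of the delay. Assume that a fraction p starts d days later, on top of a uniform 28-42. The mean is 35 + p·d and the variance is 16.3 + p(1 − p)d².
- p = 0.25, d = 14: 53.1/38.5 = 1.38.
- p = 0.25, d = 21: 99.0/40.25 = 2.46.
- Dispersion crosses 1 at d of about 10.7 when p = 0.25, and at about 15 when p = 0.10.

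The values 25% and 10% are the complication rates in the Section 10.2 sample size calculation. Treating every complication as a delay is an assumption.

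**Does the planned correction work?** In 10,000 simulated trials per scenario with no true difference and 70 per arm, the type I error at nominal 5% was:

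| Scenario | Plain Poisson | Over-dispersion only | Freely estimated scale | Robust SE |
|---|---|---|---|---|
| Uniform 28-42 | 0.4% | 0.4% | 5.1% | 5.2% |
| 25% delayed 14 days | 9.6% | 5.1% | 5.1% | 5.3% |
| 25% delayed 21 days | 21.4% | 5.15% | 5.15% | 5.3% |

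The planned correction repairs the over-dispersed cases and leaves the under-dispersed case as it was. A variance that can move in both directions is close to 5% in all three.

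**The case against.** The strongest reply is that over-dispersion is the likelier case and the plan already covers it. The window is an expectation for the standard-of-care arm, not a limit on each patient, and the trial's own premise is that complications delay treatment. This stands as far as direction goes: without an SD, the documents cannot show which way the dispersion will fall. It does not justify a correction that works only one way when one that covers both costs nothing.

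A second reply is that the error in Case A is conservative: intervals too wide, few false positives, and an aim that Section 10.2 calls descriptive. That also stands and limits the weight of the point. One might add that the usual scale adjustment would shrink the SE as well, if it were applied. But Section 10.1 invokes it only for over-dispersion.

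A reader might infer more than the documents support:
- *That the window proves under-dispersion.* It does so only if it describes individual patients.
- *That the plan states wrong error bars.* It states none for this outcome.
- *That coverage could fall to 59-75%.* Those figures need an SD of 10-14 days (dispersion 2.9-5.6 at a mean of 35) with the planned adjustment left out, which would depart from Section 10.1. The lack of a criterion for applying it is a gap in wording.
- *That the result changes with the time unit.* With the scale held at 1, a contrast of 35 versus 37 days has SE(log ratio) = sqrt(1/2450 + 1/2590) = 0.0282 and z = 0.0556/0.0282 = 1.97. In weeks, z = 1.97/sqrt(7) = 0.75. But Section 10.1 fixes the unit as days, and an estimated scale removes the effect.
- *That Poisson regression cannot give a difference in days.* No link is named, and even a log-link model yields fitted mean days per arm, which can be subtracted.

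**Conclusion.** The point holds in a limited form. The variance correction is one-directional and conditional, for an outcome whose variance has no reason to equal its mean. If starts fall within 28-42 days in both arms with a mean of 35, the interval is about 1.5-1.7 times too wide, coverage is about 99.6-99.9%, and the plan as written does not repair it. If delays are large and frequent enough, as in Case B, the planned correction is adequate when applied. Which case applies rests on a spread that the documents do not give. The consequence is confined to the precision of one secondary estimate; the primary comparison of wound complications is unaffected. How to handle patients who have not started therapy is a separate question and is not judged here.

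**What to change.** In Section 10.1, replace the conditional over-dispersion clause with: *using robust (sandwich) standard errors in all cases*. A freely estimated scale in all cases is an acceptable alternative; name one of the two before the data are seen. Add: *the model-based difference in mean days between arms will be reported with its 95% confidence interval*, because Section 10.2 asks for differences.

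The cost is one sentence and a standard option in the software already planned, with no new data and no change to sample size. Replacing Poisson by linear regression with robust standard errors would also work, but that is a preference and is not needed to resolve this point.

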10.2 Sample Size Calculations

As stated in the Section 4, we retrospective chart review of this patient population found 25% rate of wound complications. Group sizes of 97 each (194 total) achieves 80% power to detect a difference between the group proportions of -0.15; in other words, assuming the standard of care group has a complication rate of 25%, we could detect a complication rate in the NPWT group of 10% as being statistically significantly lower using a two-sized Z-test with a significance level of 0.05. This represents a clinically significant change in complication rates while remaining a feasible number to recruit within the study sites. Our proposed sample size is therefore 200 (100 in each group).

The secondary aim is not to formally test hypotheses but rather to describe this outcome and calculate preliminary estimates of differences. Among women undergoing this procedure at our study sites, approximately 70% will be

diagnosed with a malignancy, resulting in a sample size of 140 for this analysis. Among women in the standard of care group, we anticipate they will begin adjuvant therapy within 4-6 weeks after surgery. This sample size is more than sufficient (>90% power) to detect a difference of 1 day in time between surgery and beginning adjuvant therapy.

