4.0 Wound Complications at the University Of Minnesota

We performed a retrospective chart review of all patients with a $BMI \geq 30 \text{ kg/m}^2$ who have undergone a laparotomy for a known or suspected gynecologic malignancy at our institution in the past 6 months. We found that of 51 obese patients to undergo a laparotomy, 13 (25%) had some form of wound complication, either a wound dehiscence or infection. This is on par with what is reported in the literature. Further, 5 of the 51 patients were readmitted to the University of Minnesota hospital due to their wound complications, for a readmission rate of almost 10%. The results of this chart review were used to inform our sample size calculations.

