6.0 Patient Selection

Study entry is open to adult patients regardless of gender, race or ethnic background. While there will be every effort to seek out and include minority patients, the patient population is expected to mirror the obese patient population at the University Of Minnesota.

Inclusion Criteria

- 6.1 Known or suspected gynecologic or other abdominal malignancy (such as colorectal, liver, pancreatic, kidney and stomach) for which laparotomy is planned
- 6.2 Obese – defined as a Body Mass Index (BMI) ≥ 35 kg/m² as calculated in the Epic computer record
- 6.3 18 years of age or older
- 6.4 Able and willing to provide written consent

Exclusion Criteria

- 6.5 Known true tape allergy
- 6.6 Sensitivity to silver
- 6.7 History of intolerance to Negative Pressure Wound Therapy

[figure not shown]

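### Does taking the 25% complication rate from 51 gynecologic patients with BMI of 30 or more leave the sample size of 200 unsupported?

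*Combined protocol and SAP*

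**What the plan says.** Section 10.2 gives the basis of the control rate: "As stated in the Section 4, we retrospective chart review of this patient population found 25% rate of wound complications". It then states 97 per group for 80% power to detect 25% against 10% with a two-sided 5% Z-test, and rounds up to 100 per group. It defends both the target and the size: "This represents a clinically significant change in complication rates while remaining a feasible number to recruit within the study sites".

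Section 4.0 describes the source openly. The patients had BMI of at least 30 and were those "who have undergone a laparotomy for a known or suspected gynecologic malignancy at our institution in the past 6 months". The result was: "We found that of 51 obese patients to undergo a laparotomy, 13 (25%) had some form of wound complication". It adds: "The results of this chart review were used to inform our sample size calculations".

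Section 6.0 is wider on disease and sex and narrower on BMI (at least 35). On disease it admits: "Known or suspected gynecologic or other abdominal malignancy (such as colorectal, liver, pancreatic, kidney and stomach) for which laparotomy is planned". On sex: "Study entry is open to adult patients regardless of gender, race or ethnic background".

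For the secondary aim, Section 10.2 assumes a malignancy rate in words that refer to one sex: "Among women undergoing this procedure at our study sites, approximately 70% will be" diagnosed with a malignancy, giving 140 patients. The same paragraph says this aim is descriptive and is not a formal test.

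**The concern.** Section 10.2 treats the chart review as if it described the trial's own patients, and it does so only in part. The review's BMI floor is 5 units lower, it has no colorectal, liver, pancreatic, kidney or stomach cases, and it states no follow-up window, whereas Section 10.1 counts complications in the first month. Sections 1 and 3 say that complications are highly correlated with BMI and quote 34% and 34 to 40% for gynecologic oncology. That sits awkwardly with Section 4's remark that 25% agrees with the literature.

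If the true control rate were 34 to 40% and the benefit were still 15 points, 200 patients would miss it 33 to 38% of the time instead of about 20%. Section 10.2 has no sample-size re-estimation, and the annual reports in Section 11.3 do not list the pooled complication rate, so the shortfall would appear only at the end. The outcome is known within a month and accrual takes 24 months, so a mid-trial check looks easy.

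**Working it through.** **Inputs.** Two-sided 5% test, 80% power, 25% against 10%, 100 per group planned (Section 10.2); 1:1 allocation (Section 7.0); 13 of 51 (Section 4.0); literature rates of 34% and 34 to 40% (Sections 1.0 and 3.0). Complete outcomes are assumed.

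**1. The plan's figure.** With unpooled variance, n per group = (1.960 + 0.842)² × [0.25 × 0.75 + 0.10 × 0.90] / 0.15² = 7.849 × 0.2775 / 0.0225 = 96.8, so 97. This matches. With variance pooled under the null, as in the chi-squared test, n = [1.960 × √(2 × 0.175 × 0.825) + 0.842 × √0.2775]² / 0.0225 = 99.5, so 100. Power at 100 per group is 80.2% by this formula and 81.6% by exact enumeration.

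**2. Uncertainty in the rate.** 13/51 = 25.5%, exact 95% interval 14.3 to 39.6%. The 34% figure lies inside it, and 40% is at its edge.

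**3. Other control rates.** The planned effect is both a 15-point difference and a 60% relative reduction (0.15 / 0.25). The two part company once the control rate moves. Power is at 100 per group, pooled formula:

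| Control rate | NPWT rate, 15 points | Power | Total N for 80% | NPWT rate, 60% reduction | Power | Total N for 80% |
|---|---|---|---|---|---|---|
| 16% | 1% | 97% | 108 | 6.4% | 58% | 338 |
| 20% | 5% | 90% | 152 | 8% | 69% | 262 |
| 25% | 10% | 80% | 200 | 10% | 80% | 200 |
| 30% | 15% | 72% | 242 | 12% | 88% | 160 |
| 34% | 19% | 67% | 270 | 13.6% | 93% | 136 |
| 40% | 25% | 62% | 304 | 16% | 97% | 108 |

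The 108 in the 15-point column needs a 1% complication rate on NPWT, a 94% relative reduction (0.15 / 0.16). It is no realistic guide to N.

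**4. Validity and precision.** A wrong planning rate does not bias the comparison. The exact type I error of the fixed design is 4.9 to 5.2% for null rates from 10 to 40%. The 95% half-width for the difference, 1.96 × √([p₁(1 − p₁) + p₂(1 − p₂)] / 100), is 10.3 points at 25/10, 12.1 at 34/19 and 12.8 at 40/25.

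**5. What a blinded check would deliver.** A pooled 17.5% fits 25/10, 20/15 or 17.5/17.5 equally well. After 100 outcomes its 95% interval is 17.5 ± 1.96 × √(0.175 × 0.825 / 100), or 10.1 to 24.9%, which corresponds to N from about 124 to 260 even with 15 points held fixed.

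Simulated with a floor of 200 and an assumed cap of 300, the check restores 15-point power to 80% at a 34% control rate and 79% at 40% (mean N 269 and 293). When 25/10 is exactly right, about 49% of trials are enlarged and exact power rises only from 81.6 to 83.2%. With no effect at 25%, mean N is 260. With a 60% reduction, a 40% control rate takes mean N to 277 where 200 already gives 97%; at 16%, power barely moves (59.5 to 59.7%).

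**6. Cost.** Accrual is 200 / 24 = 8.3 per month, so 100 extra patients take about 12 months.

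**7. The 70%.** 0.70 × 200 = 140 patients for the descriptive aim. It does not enter the calculation of N.

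**The case for a change.** The strongest case for a change is that Section 10.2 writes its target as an absolute difference of 15 points and calls that clinically significant. On that scale, the documents' own literature rates give 62 to 67% power. The BMI correlation that the protocol cites, together with the higher BMI floor, points towards a control rate above 25%. A blinded look uses no arm-level data, keeps the type I error at 4.8 to 5.2% in simulation, and would protect the stated target.

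Much of this stands. The source does not fully match the trial population, the arithmetic is right, and the upper side is the material risk on the absolute scale. It does not carry the conclusion, for three reasons. First, Section 10.2 states 15 points jointly with 25% and 10%, and does not say that the target stays at 15 points for any other control rate. Sections 1 and 3 describe earlier NPWT results as ratios (a 40% decrease, a 4-fold decrease), and on a ratio scale a higher control rate raises power. Second, the documents give no complication rate for the added cancers, so the net shift is unknown. Third, the literature rates describe gynecologic oncology patients elsewhere. Preferring recent local data from obese patients is a defensible choice.

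**Conclusion.** No change follows. The stated power is delivered at the stated rates, and the documents do not show that the trial is under- or overpowered. Gynecologic patients with BMI of at least 35 belong to both the chart review and the trial, and Section 4 discloses the review's size, BMI limit, disease group and event count. A reader of Section 10.2 who follows its cross-reference can see what the 25% rests on. The description there is loose, but correcting it would alter no number.

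The rate could plausibly be anywhere from about 14 to 40%. Over 16 to 40%, power at 100 per group runs from 97 down to 62% for a fixed 15 points and from 58 up to 97% for a fixed 60% reduction. Re-estimation from the pooled rate helps in only one of these cases and enlarges the trial needlessly in the other. A fixed 200, tied to recruitment feasibility, is a fair trade-off against up to 100 more patients and 12 more months. The words about women in the 70% assumption are at most a drafting slip, since the figure has no stated source and feeds only a descriptive aim.

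This rests on complete outcomes, 1:1 groups and, for the re-estimation figures, an assumed look at 100 outcomes and a cap of 300. The documents specify neither the look nor the cap.

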8.5 Duration of Study Participation

It is expected the duration of study participation will be less than 2 months.

All patients will be assessed for wound complications (including infection, dehiscence and evisceration) at their 1st post-operative visit approximately 10-14 days after surgery.

Patients will continue to be tracked for wound complications for a minimum of 4 weeks after surgery by review of clinic notes/medical records. For patients who develop a wound complication, the type of complication, treatment received and outcomes will be captured.

For patients with a cancer diagnosis that requires anti-cancer therapy (chemotherapy and/or radiation), the therapy start date of therapy will be recorded.

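### Section 10.2 claims more than 90% power for a 1-day difference in time to adjuvant therapy; under the plan's Poisson model the power is about 15-20%

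*Combined protocol and SAP*

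**What the plan says.** Section 10.2 takes 70% of the 200 randomized patients as "diagnosed with a malignancy, resulting in a sample size of 140 for this analysis". For the standard-of-care arm it says "we anticipate they will begin adjuvant therapy within 4-6 weeks after surgery". It then concludes: "This sample size is more than sufficient (>90% power) to detect a difference of 1 day in time between surgery and beginning adjuvant therapy". No standard deviation, test or sidedness accompanies that figure.

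The same paragraph opens with "The secondary aim is not to formally test hypotheses but rather to describe this outcome". Section 10.1, however, says that the effect of NPWT on the number of days "will be assessed using Poisson regression, adjusting for over-dispersion if necessary", and adds: "For all analyses, p-values of less than 0.05 will be considered statistically significant". It makes no exception for the secondary aim.

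Section 8.5 limits the recording of a therapy start date: "For patients with a cancer diagnosis that requires anti-cancer therapy". The 140 in Section 10.2 counts everyone with a malignancy, whether or not adjuvant therapy is needed.

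**The concern.** A 1-day difference is small against an outcome centred on four to six weeks, and 70 patients per arm is a modest number for detecting it. A power above 90% would require start times to be almost uniform between patients. The planned Poisson model implies much more variation than that.

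The figure matters for reading the result. Time to adjuvant therapy is the only secondary objective and one of the two comparisons listed in Section 2.0, and Section 3.0 links treatment delay to survival. With the stated power, a non-significant result would look like good evidence that NPWT does not shift the start of therapy by even a day. If true power is 15-20%, a real 1-day difference would be missed in about 80-85% of such trials, and a null result would say very little about it.

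**Working it through.** **Inputs from the document**
- 140 patients in total (Section 10.2) and 1:1 allocation (Section 7.0), so n = 70 per arm.
- Control start of therapy at 4-6 weeks (Section 10.2), i.e. 28-42 days, midpoint 35.
- Poisson regression on days (Section 10.1), so variance = mean, or more if over-dispersed.
- Significance level 0.05 (Section 10.1). Two-sided is assumed here, as for the primary test.

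**Attempt to reproduce the stated figure**

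With 70 per arm, no reading that was tried reaches 90%. Values of 90% or more appeared only with more patients per arm than the plan gives. For example, 140 per arm with a standard deviation (SD) of 14/6 = 2.33 days gives 94.8%. That may be how the figure arose, but Section 10.2 gives 140 as the total.

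**Reading 1: 4-6 weeks is the mean, with Poisson variance**

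SE = sqrt(2 × mean / 70). Power = Φ(1/SE − 1.96) + Φ(−1/SE − 1.96). The 95% interval half-width is 1.96 × SE. The difference detectable with 90% power is (1.96 + 1.2816) × SE. The n per arm for 90% power at 1 day is 2 × mean × (1.96 + 1.2816)².

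| Mean (days) | SD (days) | SE (days) | Power for 1 day | Half-width (days) | 90%-power difference (days) | n per arm, about |
|---|---|---|---|---|---|---|
| 28 | 5.3 | 0.894 | 20.1% | 1.75 | 2.90 | 589 |
| 35 | 5.9 | 1.000 | 17.0% | 1.96 | 3.24 | 736 |
| 42 | 6.5 | 1.095 | 15.0% | 2.15 | 3.55 | 883 |

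The log-rate scale, which is the usual one for Poisson regression, gives 20.3%, 17.0% and 14.9% when the NPWT mean is one day shorter. Simulation of that test (200,000 trials per mean) gives 20.5%, 17.3% and 15.0%. Using the shorter mean for the second arm's variance lowers the required n to about 578, 726 and 873 per arm.

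**Reading 2: 4-6 weeks is the spread of individual start times**

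The window is 14 days wide. The SDs below are assumptions about its shape. SE = SD × sqrt(2/70).

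| Assumed shape | SD (days) | SE (days) | Power for 1 day |
|---|---|---|---|
| Uniform, 14/√12 | 4.04 | 0.683 | 31% |
| Range/4 | 3.50 | 0.592 | 39% |
| Range/6 | 2.33 | 0.394 | 72% |

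A one-sided test in the most favourable row reaches 81%.

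**What 90% would require**

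SD = 1 / (3.2415 × sqrt(2/70)) = 1.825 days, a variance of 3.33. Against means of 28, 35 and 42 days that is 11.9%, 9.5% and 7.9% of the Poisson variance. Section 10.1 makes provision for variance above Poisson, not below it.

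**Sensitivity**
- All 200 patients contributing (100 per arm): 26.7%, 22.3% and 19.4% under Poisson variance, and 86% at SD 2.33.
- Variance twice the mean (assumed): power 12.4%, 10.9% and 9.9%; half-width 2.48, 2.77 and 3.04 days.
- 50 per arm needing therapy (assumed): Poisson power 15.7%, 13.5% and 12.1%; half-width 2.07, 2.32 and 2.54 days.

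**The case against.** The strongest reply is that little depends on this figure. Section 10.2 calls the secondary aim descriptive, the trial size comes from the primary endpoint alone, and no decision in the conduct of the trial uses the 1-day claim. The published estimate and its interval would show the true precision whatever the protocol says. This stands as a limit on the consequences. It does not rescue the sentence: the same paragraph states a power, power has meaning only for a test, and Section 10.1 applies the 0.05 threshold without exempting this comparison.

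A second reply is that the plan gives no standard deviation, so the figure is strictly unsupported rather than disproved. The Poisson model is named for the analysis, not as the basis of the power, and the window-based standard deviations are assumptions. That is fair, and it is why several readings were tried. The required value of about 1.8 days (about 2.0 one-sided) still lies below all of them.

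Third, the 72% ceiling is conditional on a two-sided test with 70 per arm, and over-dispersion is allowed for in Section 10.1 rather than predicted. Both qualifications are correct, and neither brings the power to 90%.

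**Conclusion.** The power statement is wrong as written. With 70 per arm and a two-sided 0.05 test, power for a 1-day difference is about 15-20% under Poisson variance at means of 28-42 days. It is at most 72% (81% one-sided) on the most favourable reading of the 4-6 week window that was tried. The Poisson result uses only the plan's own inputs plus two-sidedness; the window-based results rest on assumed shapes. The true figure may be lower still if the data are over-dispersed or if some patients with a malignancy need no adjuvant therapy; the plan gives no proportion for the latter. The error does not touch the primary analysis or the sample size, but it should be corrected before the secondary result is interpreted.

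**What to change.** Delete the power sentence in Section 10.2 and state the precision the trial can achieve, with its assumption. Suggested text: *With 70 patients per arm and Poisson variance at a mean of 28-42 days, the 95% confidence interval half-width for the difference is about 1.8-2.1 days (90% power for about 2.9-3.6 days). It will be wider with over-dispersion or if fewer patients require adjuvant therapy.*

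Add a clause to Section 10.1 saying that this comparison is reported as an estimate with a 95% confidence interval and is not subject to the 0.05 rule, which brings it into line with the descriptive aim.

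If the sponsor had a different difference or standard deviation in mind, both should be stated, together with the test and its sidedness, and the power recomputed.

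The cost is a few lines of text and a less favourable stated figure. Enrolment, procedures and the primary analysis do not change.
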